1.6. Inclusion Criteria

- 1) Participant in the SURVIVE registry
- 2) Signed consent form for PROACT
- 3) Histological diagnosis of any cancer type (patients with treated and clinically stable brain metastasis are acceptable)
- 4) Scheduled to receive anti-cancer therapy (radiation therapy is permitted)

1.7. Exclusion Criteria

- 1) Contraindication to magnetic resonance imaging (MRI)
- 2) Unable to comply with study investigations (in the judgment of the investigator)
- 3) Life expectancy less than 1 year

Note: If a patient develops a temporary contraindication (e.g. temporary tissue expanders in breast cancer patients) after the baseline MRI, follow up MRIs will be discontinued for safety for the duration in which the patient has a contraindication. However, once the patient is no longer contraindicated to receiving MRIs, the study schedule may resume with their next scheduled MRI time point from date of enrollment. Therefore, some time points may be skipped during the patient's enrollment in the study.

Also, if a patient needs a repeat MRI at any time point for any reason (i.e. panic attack during the MRI causing them to not be able to continue, unreadable images, etc.), we may repeat the MRI as long as the patient is willing.

1.8. Expected Duration

Based on an enrollment of 40 evaluable patients (a subset of the approximately 700 SURVIVE Registry patients enrolled annually across all SURVIVE participating sites) who demonstrate moderate to high risk of cardiotoxic effects during cardio-oncology treatment due to observed segmental dysfunction on baseline MyoStrain® evaluation, it is anticipated that all subjects will be enrolled within 12 months after study initiation. The study will end when the last enrolled subject completes the 36-month follow-up, data is analyzed and reports are written. Therefore, study duration is anticipated to be approximately 54 months.

2. DEVICE DESCRIPTION

For all patients undergoing a cardiac MRI, a standard non-contrast protocol will be used to acquire a full cardiac volume for chamber sizes and LVEF in the short axis as the initial scan.

2.1. MyoStrain® SENC CMR Imaging System

The MyoStrain® SENC CMR Imaging System is limited to observational evaluation within the United States. MyoStrain® has been approved with an EC Certificate according to Directive 93/42/EEC on Medical Devices, Annex II excluding Section 4 (CE 657862) in respect of: Design, development and manufacture of software for the quantification of cardiac MRI images.

Strain Encoding (SENC) MRI technology is a fast MRI scanning diagnostic test that measures the contraction of the heart muscle in one heartbeat per image plane. This means that patients can be scanned very fast while breathing, and a complete view of the ventricles' health can be obtained in less than 6 seconds. Quantitative assessment of the strength of the heart muscle can have many clinical applications, but its highest value is in the two largest heart disease populations: those patients with heart failure and coronary artery disease.

SENC is an MRI Pulse Sequence for Strain Encoding

- A pulse sequence is an algorithm that instructs the MRI scanner to acquire certain types of images. Any MRI scanner has a large number of pulse sequences for general and specialized imaging of different parts of the body. They produce images that show different anatomies, physiologies, or pathologies of the different tissues of the body. For imaging the heart, there is a group of specialized pulse sequences that can show different aspects of the heart, including, but not limited to, the structure of the heart, the motion of the heart, the tissue characterization of the muscle, the flow of the blood, the structure of the vessels, and more.
- The Strain Encoding (SENC) pulse sequence is a specialized pulse sequence that produces images of the heart muscle that reveal the underlying contraction of the muscle of a healthy heart and associated weaknesses in case of disease. The measurements of the deformations of regions within the heart muscle ("myocardium") associated by contraction and relaxation during a single heartbeat is measured by the mechanical quantity called "strain."
- Myocardial Solutions, Inc. software measures tissue deformation or "strain" from the pulse sequence images. Quantitatively, "strain" is a mechanical property of deforming objects and measured as the percentile change in spacing between two points on a deforming object. For example, when muscle contracts, the muscle length is shortened. For example, a 30% shortening of the muscle is measured as strain of negative 30%.
- Measuring the shortening of the Heart Muscle results in two parameters that SENC quantifies: circumferential and longitudinal strain. Strain measurement depends on "direction" of measuring. For measuring the contraction of the heart muscle, there are two main directions that are typically used: 1) longitudinal strain, which describes the contraction of the myocardium that contributes to the base-to-apex contraction of the heart chambers; 2) circumferential strain, which describes the contraction of heart muscle fibers around the circumference of the chambers of the heart.
- Using SENC, segmental circumferential and longitudinal strain values in 37 regions are measured in 6 seconds.

The Intended Use of the MyoStrain® SENC MRI acquisition is:

- MyoStrain® SENC software receives image data from MRI storage archives and performs viewing, image manipulation, communication, printing, and quantification of images. Available measurements include longitudinal and circumferential strain to quantitatively describe the wall motion of the heart. Tools are provided for display of regional motion properties of the heart.
- A report interface is provided. Measurement tools provide information that can be output in standardized or specialized report formats. This interface makes it possible to quickly and reliably fill out a complete clinical report of a cardiac imaging exam with strain. The results of the measurement tools are interpreted by the physician and can be communicated to referring physicians to support the determination of a diagnosis.

2.2. Background Clinical & Preclinical Testing

Myocardial Solutions, Inc. (MSI) MyoStrain® Software was implemented with SENC MRI acquisition using source codes that were developed at Johns Hopkins University. Both Diagnosoft, before, and MSI, today, continue to use the original SENC strain source code. SENC pulse sequence patches, derived from the SENC source code, designed for Philips MRI Scanners, have been validated with extensive clinical and preclinical testing.

The MSI software leverages prior SENC image acquisition and processing functions that have been extensively studied on volunteers, phantoms studies, and clinical applications. The Fast SENC software processes images obtained with the well-studied SENC pulse sequence patch, which has supported several publications demonstrating the utility of strain imaging for various clinical applications.

Implementation of the SENC MRI acquisition in the Myocardial Solutions SENC Software has been validated as evidenced by literature across three separate comparisons: Comparisons with 1) Diagnosoft HARP, a 510k FDA certified software for measuring strain from tagged MR images; 2) Echopac STE, a certified software from GE Vingmed for measuring strain using speckle tracking methods; and 3) various physiological and pathological indicators.

Validation of MyoStrain® SENC relative to Diagnosoft HARP

1. Diagnosoft HARP is a 510k certified software for the analysis of MR Tagging images of the heart and measuring the strain that reveals the deformation of the myocardium as the heart muscle contracts and relaxes. Diagnosoft HARP is considered to be the gold standard for measuring regional strain and there are over 100 peer-reviewed published studies on the use of strain from HARP.
2. Published Comparisons: SENC versus Diagnosoft HARP compared the strain measurements from SENC to strain calculated by MR Tagging and Diagnosoft HARP software. [4] [5] [6] The comparisons

showed strong correlation in measurements of strain, both regional and global, and also the different strain measurements, such as longitudinal and circumferential strain; the correlation between SENC and tagged MRI was significant with $R=0.90$.

3. The published literature demonstrates that SENC strain measurements are comparable to those obtained using MR Tagging and HARP software, which is considered to be the gold standard method for measuring strain. SENC strain software has advantages over HARP software by providing the comparable strain results with faster acquisition and analysis. The SENC strain test takes as little as 10 minutes including analysis, which can be performed by a technologist, while HARP would require much longer testing and more specialized expertise to analyze. SENC strain is much more patient- and user-friendly requiring only a single heartbeat for image acquisition, eliminating the need for patient breath holding.

Comparison of SENC to EchoPAC, GE Vingmed STE

4. EchoPAC is a 510k and CE Mark certified package from GE Vingmed for the processing of echocardiographic images and films. It can measure the deformation and strain of tissue using speckle tracking echocardiography (STE), which is an image post-processing algorithm.
5. Published Comparisons: SENC versus EchoPAC STE compares the strain measurements from SENC to the strain calculated using Tissue Strain Echocardiography (STE). [7] STE was calculated using EchoPAC software from GE.
6. Cardiac MRI measurements of strain using SENC and MR tagging are considered to be equivalent to STE or better due to the excellent image of cardiac tissue by MRI and creation of actual physical markers inside the tissue to measure strain. STE is an image processing method that tries to extract motion and strain from conventional echocardiographic movies with their known image quality limitations.
7. The published comparisons showed a correlation between strain measurements obtained by SENC and those calculated by STE. It is important to point out that MRI, as a gold standard method, was used as the reference for measuring strain. STE post-processing calculations were expected to be inherently inferior as it inherits some of the suboptimal image qualities of echocardiography (relative to MRI).

Validation of MyoStrain® SENC Based on Clinical Physiological and Pathological Indicators

8. SENC strain was directly compared to different physiological and pathological indicators to understand the mechanics of the heart muscle and alterations due to underlying disease and pathology. This includes the understanding of the contraction of the left and right ventricles, changes in strain in the case of myocardial infarction as determined using delayed enhancement methods, and detection of ischemia in patients by utilizing stress testing.
9. Published Comparisons: SENC Strain for Physiological and Pathological Indicators. Different studies were done using SENC to understand the mechanics of the heart wall muscle and the changes that accompany certain diseases. In the case of coronary artery diseases, the studies showed changes in strain because of acute coronary artery syndrome that results in myocardial infarction.
10. Stress testing for ischemia, performed on patients with suspected or known ischemic heart disease, demonstrated that measured strain was more sensitive in detecting stenosis in the coronary arteries compared to 1) conventional cine movies with qualitative assessment of abnormal wall motion under stress, and 2) the outcomes of revascularization of positively diagnosed patients. [8][9][10][11][12]
11. Myocardial infarction studies show the value of strain measurements in assessing, with high accuracy, changes in regional function associated with damage from myocardial infarction. [13][14][15][16] Quantification of changes in contraction is more accurate (more sensitive and specific) in associating with the depth of damage vis-à-vis subjective wall motion assessment. Figure 1 shows the composite strain scale based on comparison to late gadolinium enhancement analysis to differentiate segmental myocardial function into healthy with normal contraction (defined as normokinesia and hyperkinesia), at risk with abnormal contraction (hypokinesia), and impaired viability (akinesia and dyskinesia).

[figure not shown]

Figure 1 – MyoStrain® Segmental Scale of Myocardial Health

12. Cardiac mechanics studies illustrated other applications of SENC strain measurements in understanding the mechanics of the heart, especially the left and right ventricles. [17] [18] [19] [20] [21] These healthy subjects studies demonstrated, with high accuracy and precision, the ability to detect subtle variations in regional contraction. Also, quantification revealed variations in contractility as a result of diseases affecting the right ventricle, which is very hard to assess using echocardiography because of the position of the right ventricle close to the ribs and the sternum and its geometry.

2.3. PROACT Pilot Clinical Testing

A single center, pilot study was performed to evaluate the ability of the MyoStrain® MRI software system to identify cardiotoxicity during cardio-oncology treatment of breast cancer and lymphoma patients. An interim analysis of 15 subjects from the PROACT Pilot study (VAL-1005P) is included below to provide additional clinical evidence that the MyoStrain® software is able to detect progression of myocardial dysfunction resulting from cardiotoxicity. The pilot study was performed by Principal Investigator Hr. Priv.-Doz. [name] (Facharzt für Innere Medizin, Kardiologie PD DR) at Marien Krankenhaus GmbH (Hamburg, Germany).

- **Patient Demographics**

Demographic	Average ± St Dev
Age (years)	52.2 ± 11.5
Body Surface Area (m ²)	1.8 ± 0.2
Body Mass Index (kg/m ²)	25.7 ± 4.7
History of Cancer (months)	1.4 ± 0.8
Charlson Comorbidity Index	1.4 ± 1.0

- **Baseline CMR Information**

Baseline CMR Information	Average ± St Dev
LVEF (%)	58.8 ± 5.3
LVEDV Index (ml/m ²)	77.6 ± 13.4
LVESV Index (ml/m ²)	32.1 ± 8.0
Stroke Volume Index (ml/m ²)	45.5 ± 7.8
T1 Value Pre-Contrast (msec)	1052.4 ± 44.6
T1 St Dev Pre-Contrast (msec)	52.4 ± 11.8
Global Longitudinal Strain (%)	-20.8 ± 1.9
Global Circumferential Strain (%)	-19.0 ± 1.8

# Segments > -10%	1.7 ± 1.5
# Segments > -17%	8.5 ± 4.7

- Baseline Risk Assessment of Developing Cardiotoxicity by Segmental MyoStrain®.** Patients were stratified as to their risk by the number of dysfunctional (> -10%) and abnormal segments (> -17%). These thresholds have been validated as previously described in Figure 1 above.

[figure not shown]
Cardiotoxicity Risk Level	Segmental MyoStrain® Criteria	Incidence
Low	≤ 1 Segment > -10% & < 9 Segments > -17%	46% (7/15)
Moderate	2-3 Segments > -10% or 9+ Segments > -17%	27% (4/15)
High	3+ Segments > -10% & 10+ Segments > -17%	27% (4/15)

- Baseline Echocardiography Data**

[figure not shown]
Baseline Echocardiography Data	Average \pm St Dev
LVEF (%)	63.9 ± 5.8
LVEDV Index (ml/m ²)	47.7 ± 10.1
LVESV Index (ml/m ²)	17.3 ± 6.4
Stroke Volume Index (ml/m ²)	30.3 ± 5.1
GLS (%)	-26.5 ± 14.6
E/E'	8.8 ± 2.0

Pts with Poor Acoustic Window: 4/14 (29%)

- Interim Results of Segmental Dysfunction and Global Measures Throughout Follow-up**

[figure not shown]

- Interim Results of Global Strain Evolution Throughout Follow-up

- Example of Low Risk Patient Not Experiencing Cardiotoxicity.

[figure not shown]

The PROACT Pilot study showed the ability of MyoStrain® to quantify the progressive changes in segmental and global myocardial health during cancer treatment to detect subclinical cardiotoxic effects of chemotherapy and/or targeted treatment. In this pilot study, serial MyoStrain® scans also enabled patient management to identify patients in need of proactive cardiac protection therapy while monitoring the impact including compliance of such therapy. The ability to define risk assessment based on segmental dysfunction allows identification of patients at risk of developing cardiotoxicity to monitor those predisposed to developing new or worsening heart failure. The findings in this pilot study provide further evidence for the inclusion criteria and performance criteria of the PROACT study.

2.4. Risk Analysis and Risk Assessment

The MSI SENC MyoStrain® software has been tested and approved following ISO 14971 (Medical Devices – Application of Risk Management to Medical Devices).

Detailed risk assessments have been done by Myocardial Solutions, Inc. throughout the software development. The company routinely performs management review that include analysis of device performance, change control (design, process, labeling), and corrective and preventative action for the product.

Myocardial Solutions' risk assessment has been completed and clinical risks have been reduced as far as possible by device design, labeling, and training protocols for intended users. There are no unacceptable residual clinical risks based on the risk/benefit reviews.

3. OBJECTIVES

The primary objectives of this study are:

1. to robustly quantify myocardial function in cancer patients scheduled to receive anti-cancer therapy
2. to determine the ability of MyoStrain® testing to detect subclinical cardiac dysfunction compared to standard cardiac imaging
3. to determine the impact of MyoStrain® imaging on medical management of cardiotoxicity through early detection of at risk patients.

4. PROJECT DESCRIPTION

This study evaluates the impact of medical management of cardiotoxicity through early detection of at risk patients and management of with heart failure therapy to restore myocardial function.

SENC MyoStrain® testing will quantify changes in myocardial function at pre-defined intervals to detect the progression of cardiotoxic effects of chemotherapy and/or targeted treatment. Cancer treatment regimens such as anthracyclines, trastuzumab, taxanes, other agents, or combination of drugs, with or without concomitant Radiotherapy, have been shown to cause cardiotoxicity leading to heart failure. [22] [23]

MRI strain testing (SENC or HARP) has been shown to detect cardiotoxicity before systemic changes occur. MRI strain has been shown to detect abnormal myocardial function in cancer patients treated with high-dose anthracycline chemotherapy despite normal systolic function by traditional measures. [24] [25] Clinical utility of SENC strain testing is to evaluate risk of heart failure, immediate or delayed, for chemotherapy to reduce adverse cardiac events in cancer patients treated with anthracyclines or other drug therapy known to cause cardiotoxicity.

5. STUDY DESIGN

5.1. Summary Protocol

Patients with any type of cancer scheduled to receive anti-cancer therapy with or without concomitant radiotherapy and enrolled in the SURVIVE Registry will be evaluated based on baseline MyoStrain® segmental dysfunction risk profile. After consenting to the PROACT study, patients will undergo a baseline MRI to determine their risk stratification for the study. This baseline MyoStrain® MRI must demonstrate 2 or more segments measuring >-10% or 9 or more segments >-17% for entrance into the study.

[figure not shown]
Eligible patients will then be randomized 1:1 into the MyoStrain® guided treatment arm versus the Myostrain® blinded observational arm, as shown in Figure 2. The treatment arm will guide patient management by augmenting standard of care with serial MyoStrain® monitoring of the impact of cancer therapy on myocardial function by providing physicians with MyoStrain® values, in addition to LVEF, LVEDV, and LVESV. In the

observational arm, physicians will only be provided with LVEF, LVEDV, and LVESV, which are clinical measurements. The standard of care assessments by cardiac MRI, will not include MyoStrain® assessments.

In order to obtain the MyoStrain® values, MRI images obtained will be uploaded de-identified to Myocardial Solutions, Inc. After the baseline scan, Myocardial Solutions, Inc. will inform research staff whether the patient met criteria for continued follow up in the study. At that time, the patient will be randomized to one of the two arms, as previously described, and Myocardial Solutions, Inc. will be made aware of the randomization result. If randomized to the blinded observational arm, no results from any cardiac MRI obtained for the study will be provided to physicians from Myocardial Solutions, Inc. If randomized to the MyoStrain® guided treatment arm, MyoStrain® results and LVEF, LVEDV, and LVESV will be provided for all cardiac MRI's obtained in the study to the physicians. Sites will also send Myocardial Solutions, Inc. de-identified information about the patients' medical history (i.e. comorbidities, past/current medications, etc.).

Patient's will continue to undergo MyoStrain® MRI testing, regardless of study arm, at 1 month (\pm 2 weeks), 3 months (\pm 2 weeks), 6 months (\pm 2 weeks), 12 months (\pm 30 days), 24 months (\pm 30 days), and 36 months (\pm 30 days) after the baseline visit. In addition to the MyoStrain® testing, patients will also be asked to complete a brief patient satisfaction questionnaire at each PROACT time point. Patient's will already be completing the EQ-5D Questionnaire and the Cardiovascular Risk Assessment Questionnaire as part of the SURVIVE Registry protocol at the baseline, 6 month, 12 month, 24 month, and 36 month time points.

In addition to Myocardial Solutions, Inc. reviewing the cardiac MRI images, due to the multi-departmental nature of this study, sites may also choose to obtain a clinical read on the research cardiac MR images obtained on the short axis, which are the same images that would be obtained in a clinical MRI, and provide only the LVEF, LVEDV, and LVESV for all subjects, regardless of randomization arm, and those values may be uploaded to the patients' medical record, if permitted. Doing so would then allow patients' oncology team access to this information in lieu of obtaining additional testing (i.e. clinical cardiac MRI's, echocardiograms, etc.) to obtain this same information.

EXAMPLE OF GENERAL PRINCIPLES FOR CLINICAL DECISIONS WITH MYOSTRAIN® RESULTS:

- Worsening segment abnormalities, consider cardio-protective therapies.
- Advise oncology about developing toxicities.
- Enhance patient education (symptom awareness).

Figure 2 – Study Flow Diagram

PROACT Schedule of Events		Baseline	1 Month (±2 weeks)	3 Month (±2 weeks)	6 Month (±2 weeks)	12 month (±30 days)	24 month (±30 days)	36 month (±30 days)
PROACT Informed Consent		✓						
Inclusion/Exclusion Criteria Confirmation		✓						
MyoStrain® MRI Testing		✓	✓	✓	✓	✓	✓	✓
Randomization		✓						
Patient Satisfaction Questionnaire		✓	✓	✓	✓	✓	✓	✓

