5.2. MyoStrain® Testing Methodology

System setup and testing methodology will follow the Myocardial Solutions SENC User's Manual 4.1. The SENC MyoStrain® Test procedure is a quick and simple analysis which will require only one series of images. The importation of the images from the scanner and organization of these images is mostly automated and requires very minimal interaction to function correctly. The workflow of the SENC MyoStrain® test requires only one scan and analysis phase allowing the complete scan to be completed with 6 heartbeats after imaging planning without breath-holds.

1. Use Preview mode for discovery and planning

- Before the actual analysis begins, the operator will use Preview mode to perform image planning and ensure the scanner is looking in the correct location and the myocardium is being imaged properly.
- After using Preview mode, the operator will switch the mode to Strain before acquiring more images or beginning the exam by clicking the Strain button found above the Report section

2. Select one slice from the Image List

3. Identify view and locate end-systole

4. Draw epicardial and endocardial contours on the myocardium

- To ensure accurate analysis of any view of the heart, the operator will draw a contoured mesh around the heart tissue. The mesh will quantify the entire LV of the current view and automatically segment the heart using the standard AHA model. This is done by drawing a contour on both the epicardial and endocardial edges of the left ventricle. The mesh application should be performed on each slice/view available.
- NOTE: When computing the strain after segmenting the heart with a mesh, the strain measurements are restricted within the mesh.

5. Repeat steps 2-4 for each image in Image List

6. After all images have been analyzed, complete the report and Export to PDF

- The Report Page automatically composes a report from the various sources of information that are obtained during the analysis. This report can then be uploaded, exported as a PDF document, or printed out for review.

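### Section 5.1 gives the manufacturer each patient's arm before any follow-up scan exists, and nothing in the plan masks whoever reads the 6-month segment count on which the trial is powered

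*Combined protocol and SAP*

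**What the plan says.** Section 5.1 sets this order of events.

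- Images go to the manufacturer: "In order to obtain the MyoStrain® values, MRI images obtained will be uploaded de-identified to Myocardial Solutions, Inc".
- The manufacturer judges the baseline scan: "Myocardial Solutions, Inc. will inform research staff whether the patient met criteria for continued follow up in the study".
- The patient is randomized at that point, and "Myocardial Solutions, Inc. will be made aware of the randomization result".
- It then releases MyoStrain results to physicians for guided-arm patients and withholds results for observational-arm patients.
- Sites also send it each patient's "medical history (i.e. comorbidities, past/current medications, etc"; no timing is given.
- Where the section lets sites add a clinical read of LVEF and volumes, it opens "In addition to Myocardial Solutions, Inc. reviewing the cardiac MRI images", so the manufacturer's own review is a standing part of the study.

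Section 5.2 describes the reading. The operator must "Identify view and locate end-systole" and then fit a mesh to each view: "This is done by drawing a contour on both the epicardial and endocardial edges of the left ventricle". Strain is computed only inside that mesh. The section refers to a User's Manual for methodology. It does not say whose staff the operator belongs to. Section 2.2 says only this: "The SENC strain test takes as little as 10 minutes including analysis, which can be performed by a technologist".

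Section 11 bases the sample size on the number of dysfunctional segments at 6 months and calls that the primary endpoint. The threshold is printed there as >17% and is read here as > -17%, as in Section 5.1. Section 1.5 names a different primary efficacy endpoint, sensitivity and accuracy of detection.

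Section 1.3 calls the study open label. The blinding that is described covers observational-arm patients and their physicians (Sections 5.1 and 11) and delays the study team's access to that arm's full data until the end (Section 11). No supplied section masks the strain reader.

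**The concern.** In an open-label trial, masked reading of stored images is the main protection for an imaging outcome that involves judgment. Here the company that makes the device obtains the outcome values and is given the arm before the first post-randomization scan. The plan does not keep that information from the person who draws the contours.

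If a reader knew the arm and read even slightly differently because of it, part of the between-arm difference in the 6-month count would reflect reading and not patient management. A larger sample would not remove such a shift; it would make it easier to declare significant. The intraclass correlations planned in Section 11 measure agreement between and within readers, so they would not reveal a shift that all readers share.

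**Working it through.** **Step 1: order of events.** Under Section 5.1 the baseline reading precedes randomization, so eligibility is judged without knowledge of the arm. Disclosure accompanies randomization. Follow-up scans come at 1, 3, 6, 12, 24 and 36 months, so each one is read after the company holds the arm.

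**Step 2: what might mask the reader.**

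| Provision | Where | What it protects |
|---|---|---|
| Images de-identified | 5.1 | Identity, not arm |
| Observational-arm results withheld | 5.1 | Treating physicians |
| Patient and doctor not told full features | 11 | Patients and physicians |
| Study team sees observational-arm strain data at the end | 11 | Study team |
| Observer variability by intraclass correlation | 11 | Agreement only; no masking stated |

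None of these covers the person who locates end-systole and draws the contours.

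**Step 3: the plan's own sample size.** Inputs from Section 11: means 16.8 and 12.8, difference 4.0; SD (4.7 + 7.8)/2 = 6.25; 90% power; 5% level, taken as two-sided. Per arm, n = 2 × 6.25² × (1.960 + 1.282)² / 4² = 51.3, or 52 when rounded up (104 in total). With 51 per arm (102 in total) normal-approximation power is 89.8%. The stated 102 is therefore reproduced, which supports these inputs and a two-sided test.

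**Step 4: illustration of a reading shift.** Sections 1.8, 5.6 and 5.7 now give 40 evaluable patients, so 20 per arm. Assume no true effect and a reading that differs between arms by b segments. The values of b are assumptions; the documents give none. For scale, 1 segment of 37 is 2.7%.

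- Standard error: 6.25 × √(2/20) = 1.976. Degrees of freedom: 38. Critical value: 2.024.
- False-positive rate = P(T > 2.024) + P(T < -2.024), where T is noncentral t with noncentrality b/1.976.

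| b | b/SE | In the direction of the shift | Opposite direction | Total |
|---|---|---|---|---|
| 0 | 0 | 2.5% | 2.5% | 5.0% |
| 0.5 | 0.253 | 4.3% | 1.4% | 5.7% |
| 1 | 0.506 | 7.1% | 0.7% | 7.8% |
| 2 | 1.012 | 16.5% | 0.2% | 16.7% |

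The figures 4.7 and 7.8 are the SDs of two different arms. If each is kept in its own arm, the standard error is √(4.7²/20 + 7.8²/20) = 2.036, and the same formula gives about 5.7%, 7.7% and 16.0% for 0.5, 1 and 2 segments.

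**The case against.** **The company is told, not the reader.** Section 5.1 informs the manufacturer for an evident operational reason: it must know whose results to release. No text says that the person drawing contours learns the arm. The Section 5.2 operator also plans the acquisition at the scanner, which fits site staff at least as well as company staff. The User's Manual is not among the documents and could contain a masking rule. All of this stands, and it limits the point to the absence of a stated safeguard. It does not remove the point, because releasing reports requires the arm and contouring does not, and the plan does not separate the two tasks.

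**The size is assumed.** This also stands. No reader-variability or shift figure is given, a half-segment shift hardly matters at 20 per arm, and no direction can be argued from the documents. A shift could shrink a true difference as easily as create a false one.

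**The outcome is only one of two called primary.** This is correct. The rates above say nothing about the sensitivity and accuracy endpoint of Section 1.5.

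A reader might go further and infer that follow-up readings are biased in the device's favour. The documents do not support that, since they show neither that a reader knows the arm nor any shift. Nor do they show that medication data reveal the arm: no timing is given, and only data sent after randomization could hint at it.

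**Conclusion.** The concern holds as a gap in the stated safeguards. The manufacturer holds the arm before every follow-up scan, the powered 6-month count is operator-dependent, and no supplied text masks whoever reads it. Arm-dependent reading is therefore permitted by the plan, though not shown to occur.

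The size is unknown. At the current 20 per arm, the false-positive rate for the Section 11 count would be about 5.7%, 7.8% or 16.7% for assumed shifts of 0.5, 1 or 2 segments, and nearly the same with arm-specific SDs. These figures assume a two-sample t test at a two-sided 5% level, no true effect and a constant shift.

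A reader might infer a larger effect by using the 102 patients still printed in Section 11, or by applying the smaller SD of 4.7 to both arms. Neither is a sound basis: the first conflicts with the current 40, and the second is a scenario that Section 11 does not describe.

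The change is worth making because it is cheap and specific. Confidence is medium, because the User's Manual and the manufacturer's internal roles cannot be seen.

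**What to change.** Amend Section 5.1 to state three things.

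1. Whoever locates end-systole, draws contours and scores follow-up scans, at the manufacturer or at a site, does not receive the arm or any medication data collected after randomization.
2. Each reading is locked before the arm is used for any purpose.
3. The arm goes only to whoever releases reports to physicians.

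If the User's Manual or current practice already ensures this, the amendment need only say so.

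If some 6-month scans have already been read by someone who knew the arm, report how many. Where an existing reader who does not know the arm is available, add a sensitivity analysis of the Section 11 comparison on masked re-readings of the image files retained under Section 15.2. The observer-variability readings in Section 11 could serve only if they cover every 6-month scan, which is not stated.

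**Cost:** amendment wording, a small separation of roles and a possible short delay in releasing guided-arm reports. No extra scan is needed. A full re-read would cover up to 40 scans and might need an additional reader. The documents give no reading time from which to cost it, because the 10 minutes in Section 2.2 is a best case for the whole strain test.
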